Standard statistical t-tests and one-way ANOVA will be performed to test for statistical significance between data groups using GraphPad Prism 8 (GraphPad, San Diego, CA, USA). $p < 0.05$ was considered significant.

To whom it may concern

Date : 15/06/2020

Subject : Vitamin D Regulates the Expression of Glucocorticoid Receptors in Blood of Severe Asthmatic Patients

I am [name] ,Principle investigator for the study (Vitamin D Regulates the Expression of Glucocorticoid Receptors in Blood of Severe Asthmatic Patients) . I am confirming that the results is relevant to the study in the record.

Results :

Top Vitamin D regulated pathways are involved in response to Steroids

To identify VitD targeted enriched pathways, we analyzed Comparative Toxicogenomics Database from thousands of experiments. Interestingly, the top enriched pathways regulated by VitD were involved in several metabolic and inflammatory processes including response to steroids, lipopolysaccharide as well as Interleukin-4, Interleukin-13 and AGE-RAGE signalling (Suppl. Figure 1). Many of those VitD targeted pathways were also targets of dexamethasone. These include pathways involved in inflammation; proliferation; pro-apoptosis, beside others (Figure S1).

VDR, NR3C1 and NR3C2 expression levels in different types of immune cells

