Activated T cells was shown to upregulate VDR, while treatment with VitD suppressed the proliferation of these cells, as well as their ability to produce IFN- γ and IL-17 cytokines.¹⁸ The level of expression of VDR in the blood of asthmatic and its association with the expression of steroid receptors relative to disease severity was not determined. To investigate that, we analyzed the expression profile of publicly available datasets (GSE69683) which has a large number of participants and detailed clinical information. A total number of 498 participants, of which 87 healthy controls, 77 moderate asthma, and 246 non-smokers severe asthma were included in the U-BIOPRED study. The differential expression of NR3C1, NR3C2, and VDR genes in the blood of patients from all groups was then determined. Patients with moderate asthma had higher levels of NR3C1 mRNA expression compared to health controls, although not to a significant level (\log_2 intensity 10.17 ± 0.29 ; $p=0.07$) (Figure 2A). When compared to moderate asthmatics, the expression of this gene, however, was significantly downregulated in severe asthmatic (\log_2 intensity 10.14 ± 0.23 versus 10.26 ± 0.21 ; $p<0.01$). NR3C2 mRNA expression was significantly downregulated in severe asthmatic compared to moderate asthma (\log_2 intensity 5.397 ± 0.727 versus 5.62 ± 0.5011 , $p<0.01$), and to healthy controls (\log_2 intensity 5.575 ± 0.5894 versus 5.397 ± 0.727 , $p=0.03$) (Figure 2B). Moderate asthmatics showed higher NR3C2 mRNA expression than healthy controls, although the difference was not significant. On the other hand, VDR mRNA expression was significantly upregulated in severe asthmatics compared to healthy controls (\log_2 intensity 8.386 ± 0.46 versus 8.206 ± 0.44 $p<0.01$), but not to moderate asthmatics (Figure 2C). Interestingly, NR3C1 mRNA expression correlated positively (Spearman $r = 0.11$, 95% confident interval=0.02007 to 0.1988 and $p = 0.01$) (Figure 2D), while NR3C2 expression correlated

negatively (Spearman $r = -0.55$, 95% confident interval = -0.5724 to -0.438 and $p < 0.0001$) with the levels of VDR expression in blood (Figure 2E).

[figure not shown]

Figure 2: NR3C1, NR3C2 and VDR mRNA expression level in the blood of subjects with severe asthma, moderate asthma, and non-asthmatics. Data was collected in the U-BIOPRED study (GSE69683).

Supplementation of vitamin D selectively favours the upregulation of GR- α receptor

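### The printed p-values for NR3C1 moderate versus healthy (0.07) and NR3C2 severe versus healthy (0.03) are not both reproduced by any one t-test or ANOVA rule tried, and the plan names no rule for pairwise comparisons

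*Combined protocol and SAP*

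**What the plan says.** Statistical Analysis gives the whole plan for group comparisons in one sentence: "Standard statistical t-tests and one-way ANOVA will be performed to test for statistical significance between data groups using GraphPad Prism 8". The threshold is 0.05. No post-hoc test, multiplicity rule or sidedness is given.

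The Results section on VDR and steroid-receptor genes by asthma severity describes the dataset as follows: "A total number of 498 participants, of which 87 healthy controls, 77 moderate asthma, and 246 non-smokers severe asthma were included". It then reports, on the log2 scale:

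- NR3C1, moderate versus healthy: "Patients with moderate asthma had higher levels of NR3C1 mRNA expression compared to health controls, although not to a significant level", with 10.17 ± 0.29 and p=0.07.
- NR3C1, severe versus moderate: 10.14 ± 0.23 against 10.26 ± 0.21, p<0.01.
- NR3C2, severe versus moderate: 5.397 ± 0.727 against 5.62 ± 0.5011, p<0.01.
- NR3C2, healthy versus severe: "5.575 ± 0.5894 versus 5.397 ± 0.727", p=0.03, called significant.

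NR3C1 severe versus healthy is not reported. The text does not say which test produced any of these p-values. The second item in the list of primary outcomes is the relation of asthma severity to steroid-receptor genes.

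**The concern.** Two comparisons in the same paragraph, from the same dataset, rest on almost the same strength of evidence but receive opposite significance calls. If one rule was applied throughout, its p-values should be recoverable, within rounding, from the printed summaries.

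The plan leaves the pairwise rule open, so a reader cannot tell whether the 0.07 and the 0.03 are on the same footing. NR3C2 is the only steroid-receptor gene reported as lower in severe asthma than in healthy controls. The claim that these receptors are downregulated in asthma, rather than only in severe compared with moderate asthma, therefore rests on that one p-value.

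**Working it through.** **Inputs** (Results, section on gene expression by severity; ± read as SD; two-sided tests)

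| Gene | Healthy (n=87) | Moderate (n=77) | Severe (n=246) |
|---|---|---|---|
| NR3C1 | 10.17 ± 0.29 | 10.26 ± 0.21 | 10.14 ± 0.23 |
| NR3C2 | 5.575 ± 0.5894 | 5.62 ± 0.5011 | 5.397 ± 0.727 |

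The value 10.17 is assigned to the healthy group because the next sentence gives the moderate mean as 10.26.

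**Formulas**

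- Welch: t = d / √(s₁²/n₁ + s₂²/n₂), with Satterthwaite df.
- Student: the same d over the two-group pooled SE, df = n₁ + n₂ − 2.
- ANOVA contrast (Fisher LSD): t = d / √(MSE(1/n₁ + 1/n₂)), df = 410 − 3 = 407, where MSE = Σ(nᵢ − 1)sᵢ² / 407. MSE is 0.0578 for NR3C1 and 0.4384 for NR3C2.
- Tukey-Kramer and Games-Howell: √2·t referred to the studentized range for 3 groups, with the ANOVA and Welch standard errors respectively.
- Bonferroni: 3 × p.

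**Attempt to reproduce p=0.07 (NR3C1, moderate versus healthy).** d = 10.26 − 10.17 = 0.09.

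- Welch: 0.09 / 0.0392 = 2.29, p = 0.023.
- Student: 0.09 / 0.0400 = 2.25, p = 0.026.
- LSD: 0.09 / 0.0376 = 2.39, p = 0.017.

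The means and SDs have two decimals, so d could lie between 0.08 and 0.10. With every mean and SD at its least favourable rounding limit, the largest unadjusted p-values are 0.051 (Student), 0.047 (Welch) and 0.038 (LSD). None reaches 0.07.

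**Attempt to reproduce p=0.03 (NR3C2, severe versus healthy).** d = 5.575 − 5.397 = 0.178.

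- Welch: 0.178 / 0.0784 = 2.27, p = 0.024.
- Student: 0.178 / 0.0866 = 2.06, p = 0.041.
- LSD: 0.178 / 0.0826 = 2.155, p = 0.032, which matches.

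**Both comparisons under one rule, at the printed values**

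| Rule | NR3C1 moderate vs healthy (printed 0.07, not significant) | NR3C2 severe vs healthy (printed 0.03, significant) | Call reversed |
|---|---|---|---|
| LSD | 0.017 | 0.032 | NR3C1 |
| Welch | 0.023 | 0.024 | NR3C1 |
| Student | 0.026 | 0.041 | NR3C1 |
| Tukey | 0.045 | 0.080 | both |
| Games-Howell | 0.060 | 0.062 | NR3C2 |
| Welch-Bonferroni | 0.069 | 0.073 | NR3C2 |
| ANOVA-Bonferroni | 0.052 | 0.095 | NR3C2 |
| Student-Bonferroni | 0.077 | 0.122 | NR3C2 |
| Dunnett versus healthy | 0.031 | 0.057 | both |
| Holm on Welch | 0.046 | 0.049 | NR3C1 |
| Benjamini-Hochberg on Welch | 0.035 | 0.036 | NR3C1 |

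No row gives 0.07 and 0.03 together. Rounding does not close the gap. The nearest approach is Benjamini-Hochberg on Welch: NR3C1 reaches 0.071 at its extreme rounding limit, while NR3C2 stays between 0.0352 and 0.0377, which would be printed as 0.04.

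**Other comparisons**

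- NR3C2 severe versus moderate (printed p<0.01): Welch 0.003, Games-Howell 0.008, LSD 0.010, Student 0.013, Tukey 0.028.
- NR3C1 severe versus moderate: Tukey 0.0005.
- NR3C1 severe versus healthy (not reported): d = 0.03, Student 0.33, Tukey 0.58.

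**Which participants were analysed.** 87 + 77 + 246 = 410, so 498 − 410 = 88 are not described. The Spearman interval for NR3C1 with VDR, 0.02007 to 0.1988, has a Fisher-z half-width of 0.0907. Then n = 1.06 / (0.0907/1.96)² + 3 ≈ 498, so the correlation used everyone. As a sensitivity check I added a fourth group of 88, assuming the severe-group SD. Tukey then gives 0.077 for NR3C1 moderate versus healthy, 0.149 for NR3C2 severe versus healthy and 0.056 for NR3C2 severe versus moderate.

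**The case against.** The strongest reply is that a single unadjusted rank test could give both values. I simulated samples forced to the printed means, SDs and group sizes and ran Mann-Whitney. With mild left skew (−0.5, my assumption) in the healthy NR3C1 values, the median p is about 0.06 (5th to 95th percentile about 0.03 to 0.13). For NR3C2 without skew the median is about 0.036 (about 0.016 to 0.075). The same paragraph reports Spearman correlations, which Statistical Analysis does not mention either, so that section may not list everything that was run. This stands. A reader might infer that no test at all can give both values, or that p=0.07 must be a multiplicity-adjusted figure; the documents support neither. A rank test would, however, depart from the stated methods and would need to be declared.

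Second, the set of groups is uncertain, and the figure that might name the test is not available here. This also stands: the recomputed p-values depend on the three stated groups having been analysed. The four-group check still does not give 0.03 for NR3C2.

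Third, the plan names t-tests, so unadjusted testing is consistent with it and Tukey is not obligatory. That is fair. But unadjusted t-tests throughout make NR3C1 moderate versus healthy significant, which contradicts the stated call.

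Fourth, the contrasts affected are those against healthy controls in public data, not the randomised comparison. That limits the weight of the point, although the outcome is listed as primary.

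**Conclusion.** The point holds for the t-test and ANOVA family named in the plan. No rule tried in it yields both p=0.07 and p=0.03, and at the printed summaries every one reverses at least one of the two significance calls. This assumes that ± is SD, that 10.17 is the healthy mean, that tests are two-sided, and that 87, 77 and 246 participants were analysed. At the rounding limits of NR3C1, Holm or Benjamini-Hochberg on Welch p-values could leave both calls standing, but without reproducing 0.03.

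Severe versus moderate stays below 0.05 for both genes under every three-group rule computed. Only the hypothetical four-group Tukey takes NR3C2 just above it (0.056).

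Two further inferences go beyond the documents. One is that adjusted and unadjusted p-values were mixed to obtain preferred calls; the text does not identify the tests, so this cannot be told. The other is that NR3C2 severe versus healthy should now be read as non-significant at 0.08; that figure is Tukey applied to summaries under an assumed grouping, and unadjusted tests keep it below 0.05.

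**What to change.** In Statistical Analysis, name one test and one all-pairs multiplicity rule for the three-group comparisons. One-way ANOVA with Tukey would do; Games-Howell is an alternative that suits the unequal NR3C2 SDs. State which groups, and how many participants in each, were analysed, and account for the other 88. If a rank test was used, say so.

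Rerun all nine comparisons (three genes by three pairs) on the public dataset under that rule, rather than taking replacement p-values from rounded summaries. Report every p-value, including NR3C1 severe versus healthy, and correct whichever call changes. If NR3C2 severe versus healthy is not significant under the chosen rule, limit the downregulation conclusion for NR3C1 and NR3C2 to severe versus moderate asthma, provided the rerun confirms that contrast. VDR is a separate result and is not covered by this restriction.

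The cost is a short reanalysis of public data and a reworded paragraph. The downside is that one or both stated calls against healthy controls may change; Tukey at the printed values would change both.

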Steroid resistance, as documented in cases of severe asthma, is associated with increased expression of the glucocorticoid receptor (GR)- β , which is an alternative splicing isoform and dominant-negative regulator of the GR- α ¹⁴. The abundance of GR- α mRNA is higher than GR- β mRNA in all normal tissues and cells. Normally, default splicing pathway leads to GR- α , while the alternative

splicing pathway that leads to GR- β is minimally activated ¹⁵. The latter pathway, however, seems to be upregulated in severe asthmatic patients ¹⁶. In chronic inflammatory diseases like asthma, upregulated blood levels of inflammatory cytokines can participate in glucocorticoid resistance and impaired GR function by modulating its translocation, DNA binding, and GR phosphorylation status [18].

As data from observational studies suggested a better control of asthma following restoration of VitD levels.

Hypothesis:

Correcting VitD levels in adult asthmatic patients could enhance steroid responsiveness by regulating blood GR- α /GR- β ratio levels.

Primary Out comes:

1. To find out the top pathways regulate Vitamin D

identify VitD targeted enriched pathways, we analyzed Comparative Toxicogenomics .Enriched Ontology Clustering for the identified genes was performed using the Metascape (a web-based tool used for comprehensive gene list annotation and analysis resource)Database from thousands of experiments.[Time Frame: 8 weeks]

2. To examine asthma severity in relation to steroid receptors genes [Time Frame: 8 weeks]

3. study the effect of vitamin D on GR- α receptor [Time Frame: 8 weeks]

4. study the effects of Vitamin D on cytokines. [Time Frame: 8 weeks]

Inclusion Criteria:

- Diagnosis of asthma
- age group between 18 and 65 years
- low level of 25-hydroxyvitamin D3 (25 D3) level less than 20ng/mL

Exclusion Criteria:

- smoker patients
- less than 18 years old
- patient on Vitamin D supplementation already

Materials and Methods

In silico identification of top genes regulated by vitamin D supplementation

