Using Comparative Toxicogenomics Database to identify the top genes influenced by vitamin D supplementation in thousands of experiments. One hundred five genes with at least five documented interactions with VitD were identified. Moreover, to explore if the identified genes are sharing common pathways, Enriched Ontology Clustering for the identified genes will be performed using the Metascape (a web-based tool used for comprehensive gene list annotation and analysis resource).

In silico determination of effect of vitamin D treatment on the expression of NR3C1 and NR3C2 in monocytes, macrophages, and dendritic cells

In order to investigate the effect of VitD supplementation on the mRNA expression of NR3C1, NR3C2 and VDR, publicly available datasets (GSE52819, GSE13762, GSE56490) will be explored as they were designed to examine the global transcriptional effect of VitD supplementation on monocytes, macrophages, and dendritic cells.

In silico determination of the mRNA expression levels, and correlations, of NR3C1, NR3C2, and VDR in the blood of asthmatic patients compared to healthy controls

We will extract from publicly available datasets (GSE69683) with a large number of participants and their detailed clinical information. To find Gene expression profiling of blood from these groups was analyzed, and the gene expression of GR (NR3C1 and NR3C2) which was determined.

Patients

To do double-blinded, randomized, placebo-controlled study of VitD supplementation on 45 asthmatics with VitD deficiency will be performed. Moderate to severe asthmatics between 18 and 65 years of age who had clinician-diagnosed asthma with 25-hydroxyvitamin D3 (25 D3) level less than 20ng/mL at the screening visit will be recruited at the Rashid Hospital, Dubai, U.A.E., and the Zayed Military Hospital, Abu Dhabi, U.A.E.

mRNA expression and cytokine expression

Whole blood will be collected in PAXgene tubes (Qiagen, Germany) for the isolation of cellular RNA. Blood specimens will be assessed for mRNA expression of Glucocorticoid receptor (GR- β and

GR- α) using qRT-PCR. Bioplex multiplex immunoassay (BioRad, CA, USA) will use to assess the protein expression of IL-17A, IL-17-F, IFN- γ , IL-4, IL-5 and TNF- α in serum obtained from patients before and after treatment.

Statistical Analysis

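### Primary outcome 2 credits NR3C1 and NR3C2 differences to asthma severity without reporting or separating background steroid treatment, and its VDR correlations pool the described groups with undescribed participants

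*Combined protocol and SAP*

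**What the plan says.** Item 2 of the primary outcomes reads "To examine asthma severity in relation to steroid receptors genes". The methods section on NR3C1, NR3C2 and VDR in asthmatic blood names the source: "We will extract from publicly available datasets (GSE69683) with a large number of participants and their detailed clinical information". The Statistical Analysis section is the only statement of method: "Standard statistical t-tests and one-way ANOVA will be performed to test for statistical significance between data groups", at a threshold of p < 0.05. It names no covariate, stratum or correlation method.

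The results section for this outcome (the one with Figure 2) gives a total of 498 participants and lists 87 healthy controls, 77 moderate asthmatics and 246 non-smoking severe asthmatics. It reports for NR3C1: "When compared to moderate asthmatics, the expression of this gene, however, was significantly downregulated in severe asthmatic" (10.14 ± 0.23 versus 10.26 ± 0.21 log2). NR3C2 is also lower in severe patients than in moderate patients and in controls. The section heading ties the lower expression to severity. One overall Spearman correlation with VDR is given per gene, without n: r = 0.11 for NR3C1 ("95% confident interval=0.02007 to 0.1988") and r = -0.55 for NR3C2 (-0.5724 to -0.438).

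**The concern.** Patients with more severe asthma may also differ in steroid treatment, and NR3C1 encodes the receptor for that drug class. The introduction itself links severe asthma with steroid resistance. A lower NR3C1 level in the severe group could therefore reflect the disease, its treatment, or both, and an unadjusted group comparison cannot tell these apart. The dataset is described as coming "with a large number of participants and their detailed clinical information", yet neither plan nor results report steroid use by group or adjust for it.

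The correlations raise a separate question: who is in them? One coefficient across healthy controls and asthmatics mixes within-group association with differences between group means. The three listed groups also do not add up to the stated total.

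At stake is what may be concluded from a declared primary outcome. The randomized trial is introduced in the results as a validation of these in silico findings, so an over-read severity effect would be carried into the trial's rationale.

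**Working it through.** **Inputs** (results section with Figure 2; ± values read as SD)
- NR3C1: severe 10.14 ± 0.23 (n = 246), moderate 10.26 ± 0.21 (n = 77).
- NR3C2: severe 5.397 ± 0.727, moderate 5.62 ± 0.5011, healthy 5.575 ± 0.5894 (n = 87).
- VDR: severe 8.386 ± 0.46, healthy 8.206 ± 0.44. The moderate value is not printed.
- A value of 10.17 ± 0.29 is attached to the moderate versus healthy NR3C1 comparison. Moderate is 10.26 in the next sentence, so I read 10.17 as healthy. This is an assumption.

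**1. Reproducing the group tests without adjustment**
- NR3C1, severe minus moderate: 10.14 - 10.26 = -0.12 log2, and 2^-0.12 = 0.92, so 8% lower. Pooled SD is 0.225 and 0.12/0.225 = 0.53 SD. Student p = 0.00006, Welch p = 0.00004 (printed: below 0.01).
- NR3C2, severe minus moderate: 5.397 - 5.62 = -0.223. Student p = 0.013, Welch p = 0.003 (printed: below 0.01).
- NR3C2, severe minus healthy: 5.397 - 5.575 = -0.178. Student p = 0.041, Welch p = 0.024 (printed: 0.03).

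The printed results are consistent with unadjusted tests.

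**2. Severe versus healthy for NR3C1**

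10.14 - 10.17 = -0.03 log2, Student p = 0.33, Welch p = 0.38. On this reading severe patients are not clearly below healthy controls; moderate patients are above both. For moderate versus healthy the same reading gives p of 0.02 to 0.03 by t-test and 0.08 by a four-group Tukey test, against 0.07 printed. The exact test used cannot be identified.

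**3. How large a steroid effect would explain the gaps?**

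The documents give no steroid use, so this is a range of assumptions. Let d be the share exposed in severe minus the share exposed in moderate. The effect per exposed patient needed to explain the whole gap is gap/d.

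| d | NR3C1, 0.12/d | NR3C2, 0.223/d |
|---|---|---|
| 0.25 | 0.48 | 0.89 |
| 0.50 | 0.24 | 0.45 |
| 0.75 | 0.16 | 0.30 |
| 1.00 | 0.12 | 0.22 |

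For NR3C1, with SD 0.23, this runs from about 2.1 SD (0.48/0.23) down to 0.5 SD (0.12/0.23).

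**4. Sample size implied by the correlation intervals**

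SE = (atanh(upper) - atanh(lower)) / (2 × 1.96).
- NR3C1-VDR: (0.20148 - 0.02007)/3.92 = 0.0463.
- NR3C2-VDR: (-0.46975 + 0.65109)/3.92 = 0.0463.

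With the Spearman variance 1.06/(n - 3), n = 1.06/SE² + 3, giving 497.9 and 498.4. With 1/(n - 3) both give about 470. The Bonett-Wright variance gives 473 and 531, which do not agree with each other. Every version exceeds 87 + 77 + 246 = 410. The remainder is 498 - 410 = 88, or 18% of 498.

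**5. Does pooling the described groups drive r?**

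I split r into between- and within-group parts (Pearson approximation, weights 246/410, 77/410 and 87/410). The between part is Σw(x_g - x̄)(v_g - v̄) / √(Var x × Var v), with total variances. The unprinted moderate VDR mean was varied from 8.20 to 8.45, with SD 0.45 assumed. At 8.30, for NR3C1, this is -0.00151/√(0.0599 × 0.2114) = -0.013. Over the range:
- NR3C1-VDR: between part -0.03 to +0.01; implied within-group r 0.14 to 0.10.
- NR3C2-VDR: between part -0.03 to -0.01; implied within-group r -0.50 to -0.52. This starts from -0.51, the Fisher midpoint of the printed interval, because -0.55 does not fit that interval.

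Nothing is printed for the 88, so their contribution cannot be computed.

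**6. Precision in narrower populations, holding r = 0.11 (assumption)**

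t = r√((n - 2)/(1 - r²)); intervals use 1.06/(n - 3).

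| Population | n | 95% interval | p |
|---|---|---|---|
| All | 498 | 0.020 to 0.199 | 0.014 |
| Three described groups | 410 | 0.010 to 0.207 | 0.026 |
| Severe only | 246 | -0.019 to 0.235 | 0.085 |

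**The case against.** The strongest reply is that outcome 2 is worded as a relation, and an unadjusted difference does describe a relation. That is fair to the outcome's wording. It does not cover the results heading, which credits severity.

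Three further objections limit the point, and all three stand.
- **Steroid exposure.** A reader might infer that severe patients are heavily treated, that controls take nothing, and that severity and drug exposure are one and the same contrast. The documents give no steroid use for any GSE69683 group, so none of this is established. Nor do the means form a simple exposure gradient: moderate patients are not below healthy controls on NR3C2 (5.62 versus 5.575), and NR3C1 is reported as higher in moderate asthma.
- **The 88.** A reader might take them to be smokers, because the severe group is labelled non-smoking and the trial's Exclusion Criteria list "smoker patients". The text never says who they are, and the trial's criteria do not govern a public dataset. It is also not stated whether the group tests left them out.
- **Pooling.** A reader might infer that mixing controls with patients created the correlations. Step 5 suggests otherwise: the described groups' mean differences shift r by about 0.03 at most.

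**Conclusion.** The point holds as a limit on interpretation. As analysed, the NR3C1 gap (-0.12 log2, about 0.5 SD) and the NR3C2 gap (-0.223 log2) cannot be assigned to severity rather than background steroid treatment. If 10.17 is the healthy value, the NR3C1 claim has no support from the healthy contrast and depends on severe versus moderate alone.

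The correlations rest on about 498 participants, at least 470. That figure is back-calculated, not stated, and it means that at least some of the 88 undescribed participants are included. For NR3C1-VDR the coefficient is small enough that its significance depends on who is counted.

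It would go too far to say that confounding has been shown or that outcome 2 has been answered wrongly. Outcomes 3 and 4, as far as they come from the randomized vitamin D comparison, do not depend on this analysis.

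**What to change.** 1. State n for each correlation, describe the 88 participants, and say whether they entered the group tests.
2. Report the NR3C1-VDR and NR3C2-VDR correlations within each group or adjusted for group, with and without the 88.
3. Report steroid use by group where the dataset records it, oral and inhaled separately and with dose if available. Add a sensitivity comparison of severe versus moderate, stratified by or adjusted for it. A yes/no oral-steroid term alone would leave inhaled exposure and dose unseparated.
4. If steroid use is not in the public record, word the conclusion as an association with severity and its treatment, and drop the claim that severity itself lowers expression.
5. Make clear which group the NR3C1 value 10.17 ± 0.29 belongs to.

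This is re-analysis of public data and needs no new patients. The cost is smaller subgroups and wider intervals: within the 246 severe patients, r = 0.11 would have an interval that includes zero.

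### The VDR correlations are reported as one unlabelled coefficient per gene pair, apparently pooled over about 498 people, so they do not answer the planned asthma-versus-healthy question

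*Combined protocol and SAP*

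**What the plan says.** In the Combined protocol and SAP, the Materials and Methods heading for the GSE69683 work announces "mRNA expression levels, and correlations, of NR3C1, NR3C2, and VDR in the blood of asthmatic patients compared to healthy controls". The paragraph under it describes expression of the receptor genes only, and Statistical Analysis lists t-tests and one-way ANOVA, with no method for correlations.

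The Results section on VDR and steroid receptor genes in asthma gives the motive: VDR expression in the blood of asthmatics and "its association with the expression of steroid receptors relative to disease severity was not determined". It describes the dataset thus: "A total number of 498 participants, of which 87 healthy controls, 77 moderate asthma, and 246 non-smokers severe asthma were included". Expression is then compared group by group. The correlations are not. The text says "NR3C1 mRNA expression correlated positively (Spearman $r = 0.11", "95% confident interval=0.02007 to 0.1988", p = 0.01. For NR3C2 with VDR it gives r = -0.55, interval -0.5724 to -0.438, p < 0.0001. Neither has an n, a group label, or separate values for asthmatics and controls. The Figure 2 legend, which covers the correlation panels D and E, describes expression "in the blood of subjects with severe asthma, moderate asthma, and non-asthmatics".

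**The concern.** Two places in the document set a question about groups: asthmatics against healthy controls in the Methods heading, and disease severity in the Results. One coefficient over everybody answers neither.

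The pooling is not harmless, because the same paragraph reports that the genes shift between groups. VDR is higher in severe asthma than in healthy controls, NR3C2 is lower in severe asthma than in both other groups, and NR3C1 is lower in severe than in moderate asthma. When two variables both move with group membership, a pooled correlation contains that movement as well as any association between people within a group. It can be larger or smaller than the within-group value, or have the opposite sign. A coefficient as small as 0.11 is the most exposed, and it belongs to NR3C1, the gene that codes for the glucocorticoid receptor.

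The reader is also not told who was counted. If the correlations and the expression comparisons beside them use different people, the two sets of results cannot be read together.

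**Working it through.** **Inputs.** All come from the Results section on VDR and steroid receptor genes: dataset 498; healthy 87, moderate 77, non-smoking severe 246; NR3C1-VDR r = 0.11, interval 0.02007 to 0.1988, p = 0.01; NR3C2-VDR r = -0.55, interval -0.5724 to -0.438. The n behind the correlations is not printed.

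**1. Headcount.**
- Named groups: 87 + 77 + 246 = 410.
- Remainder: 498 - 410 = 88, which is 88/498 = 17.7%.
- Named asthmatics: 77 + 246 = 323.
- Everyone not listed as a healthy control: 498 - 87 = 411.

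**2. Sample size from interval width.** Put the limits on the Fisher scale, z = atanh(limit), and take half the distance between them, h. With the usual Spearman variance 1.06/(n - 3), n = 3 + 1.06 × (1.96/h)². With the plain Fisher variance the 1.06 is dropped.
- NR3C1: atanh(0.1988) = 0.20149 and atanh(0.02007) = 0.02007, so h = 0.09071. Then n = 3 + 1.06 × 466.9 = 497.9; plain Fisher gives 469.9.
- NR3C2: atanh(0.5724) = 0.65109 and atanh(0.438) = 0.46975, so h = 0.09067. Then n = 498.4; plain Fisher gives 470.3.
- A third variance, (1 + r²/2)/(n - 3), gives 472.8 and 530.7.

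Every variant exceeds both 410 and 411. The Spearman form lands on the printed total of 498 from both intervals.

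**3. Reproducing the printed result.** The NR3C1 interval centres on r = 0.110. With t = r√((n - 2)/(1 - r²)), r = 0.11 and n = 498 give t = 2.46 and p = 0.014, in line with the printed 0.01. The interval at n = 498 is 0.020 to 0.199, as printed. At n = 410 it would be 0.010 to 0.207, which does not match.

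**4. Precision in smaller sets.** No group-specific r is given, so r = 0.11 is assumed in each row. Intervals use the 1.06 variance.

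| Set | n | 95% CI | p |
|---|---|---|---|
| All | 498 | 0.020 to 0.199 | 0.014 |
| Three named groups | 410 | 0.010 to 0.207 | 0.026 |
| Named asthmatics | 323 | -0.002 to 0.220 | 0.048 |
| Severe non-smokers | 246 | -0.019 to 0.235 | 0.085 |
| Healthy controls | 87 | -0.109 to 0.319 | 0.31 |

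The set of 411 gives the same p, 0.026, as 410. At n = 323 the p-value and the interval fall on opposite sides of the threshold only because they use different variance formulas; the plain Fisher interval is 0.001 to 0.217. That row is borderline.

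**5. NR3C2.** The printed r = -0.55 is not the centre of its own interval, which transforms back to -0.508. With r = -0.55 and n = 498 the interval would be about -0.610 to -0.484. This needs correcting, but the width still gives n of about 498. With either value of r at n = 323, the interval stays far from zero (-0.624 to -0.466, or -0.587 to -0.420).

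**6. Were the 88 in the expression comparisons?** For NR3C2, severe against healthy, the printed p is 0.03. Reading the ± values as standard deviations, 246 severe patients give 0.041 (pooled variance) or 0.024 (Welch). Adding all 88 to the severe group, as an assumption (246 + 88 = 334), gives 0.035 or 0.018. The printed value does not separate the two cases.

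**The case against.** The case for leniency has real content.

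- **The commitment is thin.** It stands in a section heading, where the comparison with controls could be read as applying to expression levels alone. No test of a difference between correlations is planned. This stands as a limit on what was promised, but the Results state a severity-related aim of their own, and one unlabelled coefficient does not meet it.
- **The 88 are not described.** A reader might infer that they lie outside the groups used for expression, so that the correlation rests on a different population. The documents do not support this. The Results say expression was determined for all groups, the figure legend does not limit severe asthma to non-smokers, and the check on the printed p-value is inconclusive.
- **Smoking.** A reader might infer from the non-smoker label that the 88 are smokers and should be dropped, because the trial excludes "smoker patients". That criterion governs trial enrolment. The Methods set no smoking restriction on GSE69683.
- **Importance.** A reader might take this correlation to be the basis of the trial. The Introduction rests the hypothesis on observational data on asthma control and on the GR-α/GR-β balance, and the in silico findings the trial was said to validate also include pathway, immune-cell and expression results.
- **The p-values are hypothetical.** They hold r fixed, and on that assumption p stays below 0.05 at 410 and at 323. This stands: they show the loss of precision and nothing about the true within-group association.
- **Figure panels D and E are not available here**, so group-specific values there cannot be ruled out. The text reports none.

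**Conclusion.** The point holds as a reporting and analysis gap. The stated question concerns asthma against health, and severity. The Results text gives one coefficient per gene pair, with no n or group, and both interval widths indicate about 498 people (470 or more under any variance formula tried), against 410 in the named groups. Healthy controls, asthmatics and about 88 undescribed people therefore appear to be pooled. Since the genes differ by group, the pooled value cannot show whether the link exists within asthma or differs from that in controls.

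This matters most for NR3C1 with VDR, where r is only 0.11. The NR3C2 link would remain clear at the smaller sizes if its strength is similar. It would be wrong to conclude that the NR3C1 link is absent in asthmatics: the within-group r is unknown and could be higher or lower. The estimate of n assumes that the intervals were built on the Fisher scale. This is a secondary in silico result and does not touch the randomised comparison.

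**What to change.** From the same GSE69683 extract:

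1. Report both correlations separately in asthmatics, also by severity, and in healthy controls, each with n and 95% CI, and add a Fisher z test of the difference between asthmatics and controls.
2. State who the 88 are and whether they entered the expression comparisons. Use the same participants for both analyses, with a non-smoker-only result as a sensitivity analysis.
3. If an overall coefficient is kept, state its n and adjust for group.
4. Correct the NR3C2 coefficient or its interval so that they agree.
5. Name the correlation method in Statistical Analysis.

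The work is a short re-analysis of public data. The cost is scientific: the NR3C1-VDR link may no longer be significant within asthmatics. The comparison with controls will also be imprecise. With 323 and 87 people, the standard error of the difference on the z scale is √(1.06/320 + 1.06/84) = 0.126, so its 95% CI extends about 1.96 × 0.126 = 0.25 either side. A non-significant difference should not be read as evidence that the correlations are equal.
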